1.3.4 ADCT-301-103

As of 14 April 2021, enrolment in the monotherapy part was completed; 44 patients were treated with camidanlumab tesirine monotherapy in Part 1 at 8 dose levels ranging from 20 to 150 $\mu\text{g}/\text{kg}$ administered on a 3-week treatment cycle and the MTD has not been reached.

The most frequently reported TEAEs ($\geq 20\%$ overall), regardless of grade or relationship, included: nausea (40.9%), fatigue and decreased appetite (36.4% each), constipation (29.5%), abdominal pain (27.3%), rash (22.7%). ([Puzanov, 2021](#)).

The TEAEs that have been assessed as Grade ≥ 3 were reported in 31 out of 44 (70.5%) patients. The most common Grade ≥ 3 TEAEs (observed in at least 5% of patients overall), regardless of relationship, included anemia (11.4%), abdominal pain, rash and pulmonary embolism (6.8% each).

Grade 3 autoimmune AE (colitis, immune-mediated adverse event, systemic inflammatory response syndrome) and grade 3 neurologic AE (dysphagia and asthenia), regardless of relationship, were observed in 6.8% and 4.5% of the patients, respectively.

Best overall responses were stable disease (SD) for 11 patients (25%) and progressive disease (PD) for 23 patients (52.3%); 2 patients were not evaluable (4.4%) and 8 (18.2%) had no post-baseline evaluation due to death (11.4%) or clinical progression (6.8%).

Some patients with paired biopsies showed decreased Tregs and increased Teffs:Tregs ratio in the local tumor environment, supporting a therapeutic rationale for the treatment of advanced solid tumors with camidanlumab tesirine in combination with other immune-modulating therapies ([Puzanov, 2020](#)).

At the time of this Protocol Amendment 7, the study is enrolling patients receiving camidanlumab tesirine in combination with pembrolizumab.

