4.1.3 Efficacy Analysis Set

All patients who receive at least 1 dose of study drug (refer to Protocol Section 6), have valid baseline disease assessment(s), and at least one valid post baseline disease assessment. Patients who do not have a post baseline assessment due to early clinical progression or death (after receiving study drug) will also be included.

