4.8.4 Progression-Free Survival

Progression-Free Survival (PFS) is defined as the time from first dose of study drug until disease progression (based on radiographic or clinical progression at end of treatment [EOT]/end of study [EOS]) or death due to any cause, whichever occurs first.

The censoring rules for PFS are as follow:

- For patients who are still alive at the time of analysis and without objective evidence of progression, patients will be censored at the last tumor assessment.

- For patients who receive subsequent anti-cancer therapy or procedure prior to disease progression or death, patients will be censored at the last tumor assessment on or prior to subsequent therapy or procedure.
- For patients who have no post baseline tumor assessment, and have no disease progression or death, or receive subsequent anti-cancer therapy or procedure(s), patients will be censored at the first dose date of study drug.
- A sensitivity analysis might be considered: if a clinical progression or toxicity is observed without radiographic progression assessment being confirmed, then the patient will be censored at the last tumor assessment.

The PFS will be estimated by Kaplan-Meier method. The median PFS and its 95% two-sided CI will be presented.

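### SAP 4.8.4: read literally, the third PFS censoring rule turns unscanned early clinical progression followed by new therapy into a Day 1 censoring

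*SAP*

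**What the plan says.** SAP 4.8.4 runs PFS from first dose to progression or death, whichever is first. Progression is "based on radiographic or clinical progression at end of treatment [EOT]/end of study [EOS", so clinical progression without a scan is an event in the main analysis. Three censoring rules follow.

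- Rule 1 covers patients "still alive at the time of analysis and without objective evidence of progression" and censors at the last tumor assessment.
- Rule 2 reads "For patients who receive subsequent anti-cancer therapy or procedure prior to disease progression or death" and censors at the last tumor assessment no later than that therapy.
- Rule 3 reads "For patients who have no post baseline tumor assessment, and have no disease progression or death, or receive subsequent anti-cancer therapy or procedure(s", and then "patients will be censored at the first dose date of study drug".

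A sensitivity analysis that might be done censors at the last tumor assessment "if a clinical progression or toxicity is observed without radiographic progression assessment being confirmed". No order of precedence among the rules is given.

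SAP 4.8 bases efficacy analyses on the Efficacy Analysis Set. SAP 4.1.3 requires a valid post-baseline assessment for that set, with one exception: "Patients who do not have a post baseline assessment due to early clinical progression or death (after receiving study drug) will also be included".

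Protocol 9.7.3 has neither a new-therapy rule nor a first-dose rule. It leaves further detail to the SAP, so it does not settle the reading.

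**The concern.** Rule 2 ties new-therapy censoring to therapy that comes before the event. Rule 3 names new therapy with no timing at all. The analysis set sharpens this. An unscanned patient enters it only because of early clinical progression or death, so the part of rule 3 about patients with neither is essentially empty there. In practice it is the therapy part that acts.

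Take an unscanned patient with clinical progression on Day 30 and new therapy on Day 45. The PFS definition makes this an event on Day 30, and rule 2 does not apply. Rule 3 as written makes it a censoring on Day 1. The protocol leads sites to expect this order of events: clinical progression is a reason to stop study drug (5.4.1), and the end-of-treatment visit is to come before any new anticancer treatment (4.2.3).

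The patients concerned are among the earliest failures. Removing them from the risk set on Day 1 raises the curve, and whether it happens depends on who went on to further therapy.

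**Working it through.** **Step 1. Which patients lose an event because the timing condition is missing?** Take unscanned patients in the Efficacy Analysis Set and read rule 3 as: no scan, and either no event or new therapy.

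| Sequence | PFS definition | Rule 2 | Rule 3 read literally | Event lost only through rule 3? |
|---|---|---|---|---|
| Clinical progression, no therapy | event | no | no | no |
| Clinical progression, then therapy | event | no | Day 1 censoring | **yes** |
| Therapy, then clinical progression | event | censors | supplies Day 1 as date | no |
| Death, no therapy | event | no | no | no |
| Therapy, then death | event | censors | supplies Day 1 as date | no |

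Only the second row is an added loss. In the third and fifth rows the only scan is the baseline one, so rule 3 merely supplies a usable date.

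**Step 2. Reproduce the reported figures (Protocol 1.3.4, monotherapy).** Of 44 patients, 11 had stable disease, 23 progressive disease, 2 were not evaluable and 8 "had no post-baseline evaluation due to death (11.4%) or clinical progression (6.8"%). Check: 11 + 23 + 2 + 8 = 44; 8/44 = 18.2%; 5/44 = 11.4% (deaths); 3/44 = 6.8% (clinical progression). The figures reproduce.

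**Step 3. Size.** Assume that all 8 failed before the Week 6 scan and that the other 36 were event-free and under observation until then. If m of the 3 clinical progressors later took therapy and are censored on Day 1, then 44 − m remain at risk, 8 − m have events, and the Kaplan-Meier estimate just before Week 6 is 36/(44 − m).

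- m = 0: 36/44 = 81.8%
- m = 1: 36/43 = 83.7%
- m = 2: 36/42 = 85.7%
- m = 3: 36/41 = 87.8%

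The largest shift is 87.8 − 81.8 = 6.0 points. If the 2 non-evaluable patients fall outside the analysis set for want of a valid assessment, the series is 34/42 = 81.0%, 34/41 = 82.9%, 34/40 = 85.0% and 34/39 = 87.2%. The picture is the same.

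**Step 4. The median.** Scan dates are not given, so this is an illustration. Let k of the 23 progressions fall at Day 42 and the rest at Day 84, let stable patients progress at Day 168, and censor the 2 non-evaluable patients just after Day 42. PFS after the Week 6 scan is (36 − k)/44 with no one censored on Day 1 and (36 − k)/41 with three.

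- k = 15: 21/44 = 47.7% against 21/41 = 51.2%, so the median moves from Day 42 to Day 84.
- k = 14: 22/44 is exactly 50%, so the answer depends on the convention for ties.
- k of 13 or less (23/44 = 52.3% or more either way): the median stays at Day 84.
- k of 16 or more (20/41 = 48.8% or less either way): the median stays at Day 42.

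**Step 5. Small groups.** SAP section 4 splits output by dose level and expansion group, and the groups are planned at about 16 and 14. As an illustration, if a group of 14 has one early event and it becomes a Day 1 censoring, early PFS goes from 13/14 = 92.9% to 13/13 = 100%.

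**The case against.** The best defence is that rule 3 is only a date fallback. Rules 1 and 2 both censor at the last tumor assessment, which an unscanned patient does not have after baseline. The two parts of rule 3 mirror rules 1 and 2 in order. On that reading it removes no event and agrees with the definition. This is plausible and may well be the intention. The text does not say so, however, and a programmer who follows the words gets a different curve.

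Exposure is also limited. The protocol schedules a disease assessment at end of treatment, and a patient scanned there leaves rule 3. But the scan may be skipped if one was done within 8 weeks, which a baseline scan can satisfy for an early failure. The 8 monotherapy patients are in any case already reported as having no post-baseline evaluation.

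The size is hypothetical. The documents do not say whether any of the 3 clinical progressors took new therapy, so no effect at all is possible. The SAP's stated summary is the median, not a pre-Week 6 percentage pooled over 44 patients. Both points stand.

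Correcting rule 3 alone would not be enough. Rule 1 asks for objective evidence of progression and could still censor a living, unscanned clinical progressor. This stands too, and the fix covers it.

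**Conclusion.** The point holds as a gap in wording with a real consequence under the literal reading: unscanned clinical progression followed by new therapy is an event by definition and a Day 1 censoring by rule 3. Where it acts, the bias is upward. In the reported monotherapy data it reaches 0 to 3 of 44 patients, or 81.8% to 87.8% for PFS just before Week 6. This rests on the assumptions that the 8 unscanned patients failed before that scan and that the number with later therapy, which is not given, lies anywhere from 0 to 3. The median may not move. PFS is a secondary, descriptive endpoint, and SAP section 4 plans no hypothesis test, so the weight is modest.

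A reader might infer more, and the documents do not support it:

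- That early deaths are also erased. A death that is the first event cannot be followed by therapy.
- That rule 3 can do nothing but remove events. Where therapy comes first, rule 2 already censors and rule 3 only sets the date.
- That every patient with later therapy, scanned or not, is censored on Day 1. That would leave rule 2 with no function.
- That the sponsor chose to censor clinical progressors. The SAP puts that censoring in an optional sensitivity analysis, which implies that the main analysis counts them as events.

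**What to change.** Make two changes in SAP 4.8.4.

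1. Replace rule 3 with: *Patients with no post-baseline tumor assessment who have no progression (radiographic or clinical) or death by the analysis date, or who start subsequent anti-cancer therapy before progression or death, are censored at first dose; clinical progression or death before subsequent therapy is an event on its own date.*
2. In rule 1, for the main analysis, replace the reference to objective evidence with *progression (radiographic or clinical)*, so that rule 1 does not censor the same patients. Leave censoring of unconfirmed clinical progression to the sensitivity analysis.

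The cost is two SAP sentences and no new data. PFS may become slightly less favourable, or may not change if no patient has the sequence in question.

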4.8.5 Overall Survival

Overall survival (OS) is defined as the time from first dose of study drug until death due to any cause.

For patients who are still alive or unknown at the time of analysis, patients will be censored at the date the patient was known to be alive.

The OS will be estimated by Kaplan-Meier method. The median OS and its 95% two-sided CI will be presented.

4.9 Safety Analyses

All safety analyses will be based on the Safety Analysis Set.

4.9.1 Adverse Events

4.9.1.1 Analyses of Adverse Events

An AE is defined as any untoward medical occurrence in a patient or clinical investigation subject administered a pharmaceutical product, which does not necessarily have to have a causal relationship with this treatment.

The definition of SAEs is referred to the Protocol section 8.1.

A treatment-emergent AE (TEAE) is defined as an AE that occurs or worsens in the period extending from the first dose of study drug to 30 days after the last dose of study drug in this study or start of a new anticancer therapy, whichever is earlier.

AEs will be coded according to MedDRA Version 22.0, and the severity of the toxicities will be graded according to the National Cancer Institute (NCI) Common Terminology Criteria for Adverse Events (CTCAE) Version 4.0, where applicable.

The summary of overall TEAEs includes:

- TEAEs
- Drug-related TEAEs
- Grade ≥ 3 TEAEs
- Drug-related Grade ≥ 3 TEAEs
- Serious Adverse Events (SAEs)
- Drug-related SAEs
- TEAEs leading to dose delayed, reduced or interrupted (camidanlumab tesirine or pembrolizumab)
- TEAEs leading to discontinuation of camidanlumab tesirine or pembrolizumab
- TEAEs leading to death
- Infusion related reactions

The incidence of TEAEs will be summarized by system organ class (SOC) and preferred term (PT). A subject will be counted only once within a SOC and PT, even if the subject experienced more than one AE within a specific SOC and PT. Below TEAEs will be summarized in the same fashion:

- Drug-related TEAEs by SOC and PT
- Grade ≥ 3 TEAEs by SOC and PT
- Drug-related Grade ≥ 3 TEAEs by SOC and PT
- The most common TEAEs ($\geq 10\%$ incidence) by PT
- TEAEs by SOC, PT and maximum CTCAE grade
- TEAEs by relationship to study drug, maximum CTCAE grade, SOC and PT

Listing of all AEs, including non-TEAEs, will be provided. Besides, TEAEs leading to dose reduced, delayed or interrupted (camidanlumab tesirine or pembrolizumab), TEAEs leading to discontinuation of camidanlumab tesirine or pembrolizumab, and TEAEs leading to death will also be provided.

Details on classification of AEs with missing or partial onset dates are provided in Section 6.

4.9.1.2 Dose-Limiting Toxities

Definition of DLT is referred to the Protocol section 6.5. DLTs will be summarized in each dose level in the dose-escalation part for the DLT-evaluable Analysis Set.

Listings of DLTs will be provided.

4.9.1.3 Serious Adverse Events

A post-dose AE is defined as an AE during treatment that occurs or worsens from the first dose of study drug.

Below SAEs will be summarized in both TEAE and post-dose AE:

- SAEs by PT
- SAEs by SOC and PT
- SAEs by SOC, PT and maximum CTCAE grade

Listings of SAEs will be provided.

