4.2.2 Treatment Period

The treatment period starts on the date when a patient receives the first dose of study drug and continues until end of treatment visit.

A treatment cycle is defined as 3 weeks (i.e., 21 days).

After completion of Cycle 4, the Day 8 visit is not required unless clinically indicated.

Patients may continue treatment for up to 1 year or until disease progression, unacceptable toxicity, or other discontinuation criteria (Section 5.4), whichever occurs first. Additionally, patients benefiting clinically at 1 year may continue treatment after a case by case review with the Sponsor.

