8.1.1 Adverse Events of Special Interest

For this study the following AEs, irrespective of seriousness and causality, are considered AESIs (except those clearly attributed to pembrolizumab alone):

- GBS (including variants such as acute motor and sensory axonal neuropathy)
- Polyradiculopathy
- Autonomic nervous system imbalance
- Nerve palsy
- \geq Grade 3 neurologic toxicities
- \geq Grade 3 immune-mediated toxicities. Of note, rashes will not be considered as immune-mediated skin toxicities, since they are well described toxicities of PBD-dimers; with exception for Stevens-Johnson syndrome, toxic epidermal necrolysis, acute generalized exanthematous pustulosis, exfoliative dermatitis, and drug reaction with eosinophilia and systemic symptoms (Note: immune-mediated skin toxicities will need confirmatory skin biopsy)

- Autoimmune-mediated events (such as, but not limited to, pneumonitis, hepatitis, colitis, endocrinopathies, type 1 diabetes mellitus, and nephritis/renal dysfunction)

For all AESIs it is important to provide as much information as possible: e.g., time of onset (including changes in severity), duration of events, time to resolution, and relationship to camidanlumab tesirine. It is also important to specify if any AEs are autoimmune mediated.

Adverse events of special interest will be closely monitored and followed.

8.2 Eliciting and Reporting Adverse Events/Adverse Events of Special Interest/Serious Adverse Events

Patients will be instructed to contact the Investigator at any time after ICF signature if any symptoms develop. At each study visit, patients will be asked a non-leading question to elicit any medically related changes in their well-being. Patients may also report AEs voluntarily and they will be instructed to contact the Investigator between visits if any symptoms develop or worsen.

All AEs will be reported starting when the patient provides written informed consent. Clinically significant medical conditions present at the time of ICF signature will be reported as medical history. Clinically significant medical conditions that start or worsen after ICF signature will be reported as AEs.

All AEs, AESIs, and SAEs, regardless of relationship to study drugs (camidanlumab tesirine and pembrolizumab), will be reported from the time the patient signs the ICF until 30 days after the last dose of study drug; thereafter, only related SAEs will be reported.

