4.9.1.5 Adverse Events of Special Interest

Definition of AESI is referred to the Protocol section 8.1.1.

Below AESIs will be summarized in both TEAE and post-dose AE:

- AESIs by PT
- AESIs by SOC and PT
- AESIs by SOC, PT and maximum CTCAE grade

Listings of AESIs will be provided.

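### The SAP limits a post-dose AE to one arising during treatment, so the second set of SAE and AESI tables usually ends no later than the TEAE set, and late related SAEs reach listings only

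*SAP*

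**What the plan says.** SAP 4.9.1.1 defines a TEAE as an AE that starts or worsens from first dose "to 30 days after the last dose of study drug in this study or start of a new anticancer therapy, whichever is earlier".

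SAP 4.9.1.3 adds a second category: "A post-dose AE is defined as an AE during treatment that occurs or worsens from the first dose of study drug". It then states "Below SAEs will be summarized in both TEAE and post-dose AE". SAP 4.9.1.5 repeats this for events of special interest: "Below AESIs will be summarized in both TEAE and post-dose AE". Neither section says when treatment ends for this purpose, or why a second set of tables is wanted.

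Two places in the documents offer an end of treatment:
- SAP 4.7.1 counts treatment duration from the first to the last treatment date.
- Protocol 4.2.2 says: "The treatment period starts on the date when a patient receives the first dose of study drug and continues until end of treatment visit". Under Protocol 4.2.3 that visit should come before any new anticancer treatment, and preferably, but not necessarily, within 30 days of the last dose.

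On collection, Protocol 8.2 requires all AEs, AESIs and SAEs up to 30 days after last dose, with no cut-off at new therapy; "thereafter, only related SAEs will be reported". Protocol 4.2.4 follows patients for up to 1 year from EOT.

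**The concern.** Both windows open at first dose, so only their closing dates can make the two sets of tables differ. If the post-dose window closes first, or on the same day, the second set repeats the first or shows less.

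The events at issue are delayed, drug-related and serious. The protocol gives reasons to expect some:
- Protocol 1.5 notes immune-related reactions after the last dose of pembrolizumab.
- Protocol 1.3 reports GBS or polyradiculopathy in 14 of 338 patients across the monotherapy program, though none in this trial at Amendment 7.
- Protocol 7.4.6 builds the 9.5-month contraception period from 5 half-lives plus 6 months. Relevant exposure to camidanlumab tesirine is therefore taken as 9.5 − 6 = 3.5 months. At 30 days a month that is 105 days, of which a 30-day window covers 30/105, or 29%.

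The frequency and severity of AEs and SAEs is a primary endpoint (Protocol Section 3). The tables give counts, percentages and grades by dose level and group. Listings do not.

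**Working it through.** The plan states no figure to reproduce. The check compares closing dates. Let L be the last dose of any study drug, N the start of new anticancer therapy, and EOT the date of that visit, e days after L.

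**TEAE window** (SAP 4.9.1.1): closes at the earlier of L+30 and N.

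**Post-dose window, reading A** (treatment ends at last dose, SAP 4.7.1): closes at L. That is 30 days before L+30. It could outlast the TEAE window only if N came before L, and Protocol 6.10.2 prohibits other anticancer therapy during treatment, apart from hormonal maintenance.

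**Post-dose window, reading B** (treatment ends at EOT, Protocol 4.2.2):
- If e ≤ 30 and EOT precedes N, as Protocol 4.2.3 prefers, it closes at or before the TEAE window.
- If e > 30, it can close later. Protocol 6.6.2.1 discontinues pembrolizumab once an AE hold passes 12 weeks beyond the last dose, and Protocol 6.6.1 allows camidanlumab tesirine suspensions longer than 21 days. If neither drug is given after L and EOT follows a 12-week hold, e is about 84. The post-dose window then outlasts L+30 by about 84 − 30 = 54 days.

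**Gap 1: late related SAEs.** An event starting after both EOT and L+30 is outside both windows under either reading. With 365 days of follow-up from EOT, the uncovered stretch is (e + 365) − max(e, 30):

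| EOT visit | Uncovered from | Follow-up ends | Length |
|---|---|---|---|
| e = 0 | L+30 | L+365 | 335 days |
| e = 30 | L+30 | L+395 | 365 days |
| e = 84 | L+84 | L+449 | 365 days |

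**Gap 2: early new therapy.** If N falls before L+30 and EOT precedes N, the TEAE window closes at N and the post-dose window has already closed. From N to L+30 the protocol still collects events of any cause, but neither set of tables counts them.

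**Other summaries.** The overview in SAP 4.9.1.1 has lines for SAEs and drug-related SAEs, but it is introduced as a summary of TEAEs. SAP 4.9.1.4 only lists deaths. The listings (all AEs including non-TEAEs, SAEs, AESIs, deaths) do show these events.

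**Limits of the gaps.** SAP 6.1.1 counts AEs with partial or missing dates as TEAEs, so the gaps concern dated events. After L+30 only related SAEs are collected, so for AESIs Gap 1 contains related serious ones only.

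**Illustrative size.** No late-event rate is given. If one patient in a group of 16 (the planned size of Group 1) had such an event, the incidence would be understated by 1/16 = 6.25 percentage points.

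**The case against.** The strongest reply is that this is an undefined phrase, not a wrong rule. The sentence gives no end date, and because the SAP asks for both sets, an open-ended window may have been intended. That is possible, but the words then contradict the intent, and a programmer could reasonably implement last dose, EOT or no limit.

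A second reply is that nothing is lost. Late events are listed, Protocol 9.8.1 puts the focus of AE summaries on TEAEs, the study is descriptive, and with about 95 patients a few late events can be read one by one. The two-patient GBS stopping rules (Protocol 4.3) have no 30-day limit, and recurrences of GBS are reported even after a patient completes the study. This stands: safety decisions during the trial do not depend on these tables. It does not supply the incidence and grade by dose level or group that the tables are for.

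Three stronger readings are tempting, and the documents do not support them:
- That the post-dose tables never reach past the TEAE tables. They can, as the hold example shows.
- That every related SAE after day 30 drops out. Those starting between day 30 and a late EOT would be counted under the EOT reading.
- That the SAP states these tables are for delayed events. That purpose is an inference from there being two sets.

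**Conclusion.** The point holds in a limited form and merits correction before database lock. Under either documented end of treatment, the post-dose SAE and AESI tables are usually no wider than the TEAE tables, and for patients with a late EOT their width depends on when the visit happened. Related SAEs starting after both EOT and 30 days from last dose are collected but appear in no summary table; so do SAEs and AESIs between an early new therapy and day 30 when EOT came first.

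The uncovered stretch is about 335 to 365 days per patient, assuming a full year of follow-up from EOT. The number of events is unknown, and the 6.25-point figure is only an illustration. This is an incomplete primary safety summary, not a loss of data.

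**What to change.** In SAP 4.9.1.3, delete the words during treatment and state both ends of the window. For example: *a post-dose AE is any AE with onset or worsening on or after the first dose of study drug through end of study, regardless of time since last dose or start of new anticancer therapy.* Apply the same definition to the AESI tables in 4.9.1.5.

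This needs no new data and no extra tables, but it has a small cost. Up to day 30 the table would hold events of any cause; after day 30 it would hold related SAEs only. It would also include events that follow new therapy, whose attribution is less clear. Either add a footnote saying so, or show events after day 30 or after new therapy in a separate column. The separate column is clearer, because it keeps the all-cause percentages intact.
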